2.7.1.1 Adverse events of special interest (AESI)

Hyperkalemia is the only AESI. The search strategy will be MedDRA PTs Hyperkalaemia and Blood potassium increased.

2.7.2 Deaths

Separate summaries for on-treatment and all deaths (including post-treatment death) will be produced by SOC and PT.

Advanced Accelerator Applications,	Confidential	Page 18 of 27
A Novartis company		
SAP amendment		CAAA001A12401

All deaths will be listed, post treatment deaths will be flagged. A separate listing of deaths prior to starting treatment will be provided for all screened subjects.

In case a patient died due to COVID-19, it must be clear from the eCRF if the death was due to underlying COVID-19 or a different reason. Therefore, 'Primary Cause/ Reason for Death' should indicate 'Suspected COVID-19' or 'Confirmed COVID-19'. If a test is performed after the patient died and the assessment indicates death was due to COVID-19 infection, the 'Primary Cause/ Reason for Death' should be retrospectively changed from 'Suspected COVID-19' to 'Confirmed COVID-19'. A separate presentation of deaths due to COVID-19 will be produced.

2.7.3 Laboratory data

On analyzing laboratory data, data from all sources will be combined. The summaries will include all assessments available for the lab parameters collected no later than 24 hours after the start of the LysaKare[®] infusion. The laboratory parameters that will be investigated, and the timing that the laboratory parameters will be assessed are summarized in Table 2-1.

	ematology and Chemist		incitta
Haematology (Assessment at screening, pre-dose and 24h after start of the infusion)	Blood Chemistry (serum) (Assessment at screening, pre-dose and 24h after start of the infusion)	Electrolytes (serum) (Assessment at screening, pre-dose and 2h, 4h, 6h, 8h, 12h and 24h after start of the infusion)	Venous Blood Gas (Assessment at screening, pre-dose and 2h, 4h, 6h, 8h, 12h and 24h after start of the infusion)
WBC with differential	BUN or urea	Potassium	рН
Platelets	Uric acid	Sodium	Lactate
Haemoglobin	Serum creatinine	Chloride	pCO2
Haematocrit	Creatinine clearance* Albumin Total bilirubin Alkaline phosphatases AST/ASAT ALT/ALAT	HCO3	
	Gamma-GT		
	Glucose		
	LDH		

Table 2-1 Hematology and Chemistry Laboratory Assessments

(*) Calculated using Cockcroft-Gault formula

Laboratory values outside normal ranges will be listed and flagged. The following flags will be used:

'+': 'Higher than reference value'

'-': 'Lower than reference value'

The respective parameter and the flagged value will be presented patient-wise by visit together with the reference values.

Advanced Accelerator Applications,	Confidential	Page 19 of 27
A Novartis company		
SAP amendment		CAAA001A12401

The following summaries will be produced for hematology and biochemistry laboratory data (by laboratory parameter and treatment):

- Worst post-baseline Common Toxicity Criteria (CTC) grade (regardless of the baseline status). Each subject will be counted only for the worst grade observed post-baseline.
- Shift tables using CTC grades to compare baseline to the worst on-treatment value.
- For laboratory tests where CTC grades are not defined, shift tables using the low/normal/high/(low and high) classification to compare baseline to the worst on-treatment value.

The following listings will be produced for the laboratory data:

- Listings of all laboratory data, with CTC grades and classification relative to the laboratory normal range. Lab data collected during the post-treatment period will be flagged.
- Listing of all CTC grade 3 or 4 laboratory toxicities.

Liver parameters

Liver parameters of interest are total bilirubin (TBL), alanine aminotransferase (ALT), aspartate aminotransferase (AST) and alkaline phosphatase (ALP). The number (%) of patients with worst post-baseline values as per Novartis Liver Toxicity guidelines will be summarized:

The following summaries will be produced:

- ALT or AST > 3xULN
- ALT or AST > 5xULN
- ALT or AST > 20xULN
- TBL > 2xULN
- TBL > 3xULN
- ALT or AST > 3xULN & TBL > 2xULN
- ALT or AST > 3xULN & TBL > 2xULN & ALP < 2xULN (potential Hy's law)

Potential Hy's Law events are defined as those patients with occurrence of AST or ALT > 3xULN and TBL > 2xULN, and ALP < 2xULN at initial presentation during the on-treatment period. Note that the criteria relating to combined elevations of AST (or ALT) and TBL are based on the peak values at any post-baseline time for a patient.

For patients with abnormal ALT or AST baseline values, a clinically significant liver safety signal corresponding to Hy's law is defined by: [ALT or AST > 3*baseline] OR [ALT or AST >8*ULN], whichever is lower, combined with [TBIL >2*baseline AND >2*ULN].

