3.2 Treatment Phase

On the infusion day, patients will be followed according to the assessments schedule in Table 8-1. LysaKare[®] (1,000 mL solution) will be administered intravenously for 4 hours. Before the infusion (at 0 h time point), a set of baseline tests will be performed. During and after the infusion, the patient's condition will be monitored for evaluation of any adverse events.

Patients will have an option to stay overnight in the clinic or can leave after the 12 h assessment and return to the clinic for the 24 h assessments. All patients will be discharged from the unit after the completion of the 24 h assessments.

Only patients with potassium level of ≤ 6 mmol/L at screening will be allowed to be dosed. For Poland only, only patients with potassium level of ≤ 5.5 mmol/L at screening will be allowed to be dosed. Potassium testing on the infusion day will be performed at 0 h (before the infusion), at 2 h (during the infusion) and 4 h, 6 h, 8 h, 12 h, and 24 h (after the infusion). Vital signs and ECGs will be taken as specified in the assessment schedule.

All patients will be monitored closely for signs and symptoms of hyperkalemia, e.g. dyspnoea, weakness, numbness, chest pain and cardiac manifestations (conduction abnormalities and cardiac arrhythmias).

Patients should be instructed to drink substantial quantities of water (at least 1 glass every hour) on the day of infusion to remain hydrated and facilitate excretion of excess serum potassium. Patients are permitted to void as needed.

In case of signs and symptoms of hyperkalaemia, LysaKare[®] infusion must be stopped and appropriate corrective measures must be taken. In the occurrence of severe renal insufficiency referral to hemodialysis unit should be considered per investigator discretion.

Advanced Accelerator Applications Clinical Trial Protocol (Version 01)

Confidential

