8.4.2 Laboratory Assessments

The laboratory assessments in this study require blood samples for hematology and blood chemistry, electrolytes and blood gas, as well as a pregnancy test. The full Chemistry assessments are required at Screening and on Infusion day at 0h (pre-infusion) and 24h from the start of the infusion and **must** be performed strictly on **serum** samples. Electrolyte measurements (with or without the full Chemistry assessment) are required at Screening and on Infusion day at 0h (pre-infusion) and, 2h, 4h, 6h, 8h, 12h and at 24h from the start of the infusion and **must** be performed strictly on **serum** samples. Venous blood gas (VBG) samples are required at Screening and on Infusion day at 0h (pre-infusion) and, 2h, 4h, 6h, 8h, 12h and 24h from the start of the infusion and can be performed as per site standards. The same sampling methodology should be used at all time points for consistency. Laboratory assessments will be performed at the investigational site. **Samples must be centrifuged within one hour and analyzed within 3 hours of collection to avoid degradation.** Laboratory normal ranges must be provided for all laboratory assessments.

At Screening: all patients will have screening laboratory assessments per the Table 8-1 no less than 24 hours and no more than 7 days prior to the infusion date.

Confidential

During the Treatment Phase (infusion day): a time window of +/-5% (equal to 3 min/h) is permitted for study assessments at 2h, 4h, 6h, 8h, 12h. A time window of +/-2 hours is accepted for the 24-hour assessments.

In the event of a significant laboratory abnormality, or if clinical or laboratory evidence of toxicity occurs, the Investigator will collect additional specimens for repeat or additional analyses, at intervals appropriate to the abnormality. The patient will be closely followed until sufficient information is obtained to determine the cause or the value regresses. Appropriate remedial measures should be taken, and the response recorded.

All safety laboratory results must be evaluated by the Investigator before administration of study medication.

Any clinically relevant change from baseline onwards will be recorded on the Adverse Event page of the e-CRF, possibly with a single diagnosis encompassing all related clinical changes.

Haematology	Blood Chemistry (serum)	Electrolytes (serum)	Venous blood gas		

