 Haematology (for assessment at screening, pre-dose and 24h after start of the infusion) WBC with differential Platelets Hb Haematocrit 	 Blood Chemistry (serum) (for assessments at screening, pre-dose and 24h after start of the infusion) BUN or urea Uric acid Serum creatinine Creatinine clearance (calculated using Cockcroft-Gault formula) Albumin Total bilirubin ALP AST/ASAT 	Electrolytes (serum) (for assessments at screening, pre dose and, 2h, 4h, 6h, 8h, 12h, 24h after start of the infusion) • Potassium • sodium • chloride • HCO3	Venous blood gas (for assessments at screening, pre dose and, 2h, 4h, 6h, 8h, 12h, 24h after start of the infusion) • pH • lactate • pCO2		
	 ALT/ALAT Gamma-GT Glucose LDH 				

Table 8-2. Hematology and Chemistry Laboratory Assessments

8.4.3 **Pregnancy Test**

A pregnancy test (serum or urine) must be performed at screening and prior to the start of the infusion with LysaKare[®] for every female patient of childbearing potential.

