8.4.4 ECG

Standard 12-lead ECGs will be performed. ECGs will be recorded at screening, and the 0 h, 4 h, 8 h and 24 h timepoints to measure the different ECG intervals (RR, PR, QRS, QT and QTcF).

Advanced Accelerator Applications Clinical Trial Protocol (Version 01)

Confidential

An ECG in triplicate (at least 5 minutes apart) will be taken supine, after 10 minutes rest, and not immediately after a meal. The parameters will be measured as a mean value of minimally 3 beats; the mean of each parameter has to be used for eCRF completion. The preferred sequence of cardiovascular data collection at the timepoints with multiple assessments is ECG collection first, followed by vital signs, and blood sampling.

Additional, unscheduled, safety ECGs may be repeated at the discretion of the investigator at any time during the study as clinically indicated. Unscheduled ECGs with clinically significant findings should be collected in triplicate.

The Investigator will note in the source documents (and in the eCRF) whether the ECG is normal or abnormal, as well as the clinical relevance of abnormal ECGs results and the different ECG intervals measurements, calculated using the mean value of 3 measurements for each parameter. Relevant ECG abnormalities at screening will be recorded in the medical history page, while changes during the study will be recorded on the Adverse Event page of the eCRF.

The original ECGs on non-heat-sensitive paper or a certified copy on non-heat sensitive paper, appropriately signed, must be collected and archived at the study site. Each ECG tracing should be labeled with the study number, subject initials (where regulations permit), subject number, subject date of birth, ECG date, and kept in the source documents at the study site.

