- 1. *pre-treatment period*: from day of patient's sign informed consent to the day and time before administration of study treatment.
- 2. *on-treatment period*: from date and time of administration of study treatment to 30 days after date of last administration of study treatment.
- 3. *post-treatment period*: starting at day 31 after administration of study treatment.

If dates are incomplete in a way that clear assignment to pre-, on-, and post-treatment period cannot be made, then the respective data will be assigned to the on-treatment period. Refer to Section 5.1.2 for imputation rules concerning AE start and stop dates.

Safety summaries (tables, figures) include only data from the on-treatment period with the exception of baseline data which will also be summarized where appropriate (e.g., change from baseline summaries). In addition, a separate summary for death including on treatment and post treatment deaths will be provided. In particular, summary tables for AEs will summarize only on-treatment events, with a start date during the on-treatment period (*treatment-emergent* AEs).

However, all safety data will be listed and those collected during the pre-treatment and post-treatment period will be flagged.

Windows for multiple assessments

For the definition of time windows in the treatment phase, refer to the study protocol Section 8.4.2 and Table 8-2 of the Protocol. During the Treatment Phase (infusion day): a time window of +/-5% (equal to 3 min/h) is permitted for study assessments at 2 h, 4 h, 6 h, 8 h, 12 h. A time window of +/-2 hours is accepted for the 24-hour assessments. Study assessments captured outside of the time window will still be used in any analyses and will be captured as a minor protocol deviation.

In order to summarize physical exam, vital sign, ECG, laboratory collected over time (including unscheduled visits), the assessments will be time slotted. The following general rule will be

Advanced Accelerator Applications,	Confidential	Page 11 of 27
A Novartis company		
SAP amendment		CAAA001A12401

applied in creating the assessment windows: If more than one assessment is done within the same time window, the assessment performed closest to the target date will be used. If two assessments within a time window are equidistant from the target date, then the earlier of the two assessments will be used.

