2.7.4 Other safety data

2.7.4.1 ECG data

Single standard 12-lead ECGs will be obtained using an ECG machine that automatically calculates heart rate (HR) and measures RR, PR, QRS, QT, and QTcF intervals. All ECG

Advanced Accelerator Applications,	Confidential	Page 20 of 27
A Novartis company		
SAP amendment		CAAA001A12401

assessments will be performed in the supine position. All ECG assessments will be read and interpreted locally. ECGs will be reported at screening, and at the 0h (before LysaKare[®] injection) as well as the 4h, 8h, and 24h timepoints (after LysaKare[®] injection).

Data handling

In case of ECG replicates at any assessment, the average of the ECG parameters at that assessment should be used in the analyses.

Data analysis

The number and percentage of subjects with notable ECG values will be presented.

- QT, QTcF
 - New value of > 450 and ≤ 480 ms
 - New value of > 480 and ≤ 500 ms
 - New value of > 500 ms
 - Increase from Baseline of > 30 ms to ≤ 60 ms
 - Increase from Baseline of > 60 ms
- HR
 - Increase from baseline >25% and to a value >100 bpm
 - Decrease from baseline >25% and to a value < 50 bpm
- PR
 - Increase from baseline >25% and to a value >200 ms
 - New value of > 200 ms
- QRS
 - Increase from baseline >25% and to a value > 120 ms
 - New values of QRS > 120 ms

The summaries will include all ECG assessments performed no later than 30 days after the last study treatment date.

A listing of all ECG assessments will be produced and notable (e.g. clinically significant abnormality) values will be flagged. In the listing, the assessments collected during the post-treatment period will be flagged.

For each of the ECG parameters, descriptive statistics at baseline, at each post-baseline time point and changes from baseline at each post-baseline time point will be summarized. Changes from baseline to maximum for QTcF will also be summarized.

Patients with notable ECG interval values will be listed and the corresponding notable values and abnormality findings will be included in the listings.

Unscheduled ECG measurements will not be used in computing the descriptive statistics for change from baseline at each post-baseline time point. However, they will be used in the analysis of notable ECG values.

Advanced Accelerator Applications,	Confidential	Page 21 of 27
A Novartis company		
SAP amendment		CAAA001A12401

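### SAP 2.7.3 ends laboratory summaries at 24 hours after infusion start, inside the accepted 22–26 h window for the 24 h sample and short of the SAP's own 30-day on-treatment period

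*SAP*

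**What the plan says.** SAP 2.7.3 sets the rule for laboratory tables: "The summaries will include all assessments available for the lab parameters collected no later than 24 hours after the start of the LysaKare[®] infusion".

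Other current text points elsewhere:

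- Protocol 8.4.2: "A time window of +/-2 hours is accepted for the 24-hour assessments". SAP 2.1.1 repeats this window and adds: "Study assessments captured outside of the time window will still be used in any analyses". It also assigns laboratory values, including those from unscheduled visits, to time slots for summary.
- SAP 2.1.1 restricts safety tables and figures to the on-treatment period, which runs from the start of infusion to 30 days after it.
- SAP 2.7.3 itself compares baseline with the worst value on treatment in its shift tables. Its liver subsection uses worst post-baseline values, places potential Hy's law cases in the on-treatment period, and bases the combined transaminase and bilirubin criteria on peaks at any time after baseline.
- Protocol Table 8-2 schedules haematology "for assessment at screening, pre-dose and 24h after start of the infusion", and full chemistry at the same times. Electrolytes and venous blood gas are also taken at 2, 4, 6, 8 and 12 h.

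SAP section 4, on changes to protocol-specified analyses, deals only with COVID-19 and does not explain the cut.

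**The concern.** The cut falls in the middle of the window in which the 24 h sample is valid. A sample that complies with the protocol can therefore be too late for the tables, while SAP 2.1.1 keeps even a non-compliant one. The same sentence also shuts out repeat samples taken after the 24 h visit, which protocol 8.4.2 foresees after a significant abnormality. The worst-on-treatment wording, read with SAP 2.1.1, would count them.

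Change in laboratory parameters is a stated secondary endpoint. Two programmers working from different sentences of the SAP could produce different denominators and different worst values for the haematology, chemistry and liver tables.

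**Working it through.** **1. The window against the cut.** Inputs: target 24 h and tolerance ±2 h (protocol 8.4.2, SAP 2.1.1); cut at 24 h (SAP 2.7.3).

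- Window: 24 − 2 = 22 h to 24 + 2 = 26 h, a length of 4 h.
- Part after the cut: 26 − 24 = 2 h, and 2/4 = 50%. This is a share of the window, not of patients.

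**2. What a late draw removes.**

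- Haematology and full chemistry: 1 scheduled post-dose sample; 1 − 1 = 0 left.
- Electrolytes and blood gas: 6 scheduled post-dose samples; 6 − 1 = 5 left (2 to 12 h).

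**3. A compliant draw at 25 h under each rule.**

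| Output | SAP 2.7.3 cut, read literally | Other SAP text |
|---|---|---|
| Worst-grade tables | out | in (2.1.1 window, out-of-window rule, 30-day period) |
| Shift tables | out | in (worst on-treatment value in 2.7.3, with 2.1.1) |
| Single-parameter liver counts | out | in (2.1.1) |
| Combined liver criteria | out | in (the liver subsection's own rule on peaks at any time after baseline) |
| Listings | cut does not apply | in |

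**4. Are draws after 24 h plausible?** Under protocol 3.2 patients "can leave after the 12 h assessment and return to the clinic for the 24 h assessments". Under protocol 8.4.4 the preferred order is "ECG collection first, followed by vital signs, and blood sampling", and "An ECG in triplicate (at least 5 minutes apart) will be taken supine, after 10 minutes rest".

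- Minimum time before vital signs and blood: 10 min rest + 2 gaps × 5 min = 20 min. Procedures begun at exactly 24 h give a draw at 24 h 20 min or later. To draw by 24 h they must begin by 24:00 − 0:20 = 23 h 40 min.
- SAP 2.7.4.1 describes ECG collection differently: "Single standard 12-lead ECGs will be obtained". With one ECG the latest start is 24:00 − 0:10 = 23 h 50 min.

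**5. How many patients?** The documents give no draw times. The bounds are 0 and approximately 45. Three assumed distributions, for illustration only, with 45 treated:

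- uniform over 22–26 h: 45 × 0.50 = 22.5 patients after the cut;
- normal, mean 23.5 h, SD 0.5 h: share above 24 h = 0.159; 45 × 0.159 ≈ 7;
- normal, mean 24.25 h, SD 0.5 h: share above 24 h = 0.691; 45 × 0.691 ≈ 31.

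The answer depends almost entirely on the assumption, so none of these is an estimate.

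**The case against.** The strongest reply is that 24 hours means the nominal visit. The sentence leads directly into SAP Table 2-1, whose columns use nominal times. SAP 2.1.1 slots samples to time points and keeps out-of-window values, so an in-window draw at 25 h should be kept too. On that reading nobody is lost.

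This is plausible, and it is why the lower bound is 0. But neither document says so. The sentence speaks of collection relative to infusion start, and SAP 2.7.4.1 uses the same construction for ECGs with a 30-day limit, where it can only mean elapsed time. The SAP gives no order of precedence between the general rule in 2.1.1 and the specific one in 2.7.3. The nominal reading also leaves the conflict with the 30-day period unresolved.

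The reply is right on timing: the order of procedures is preferred, not mandatory, and procedures may start from 22 h. Late draws are plausible, not shown.

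Three stronger readings are tempting but unsupported:

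- A reader might infer that the on-treatment period serves adverse events only, because SAP 2.1.1 introduces it in that context, and that the SAP is therefore silent on later repeats. The same subsection applies the period to safety tables and figures generally, and SAP 2.7.3 relies on it. The fault is a conflict between 24 hours and 30 days, not silence.
- A reader might infer that every liver summary loses the late sample. The combined criteria have their own rule, which would include it.
- A reader might infer that a longer period calls for an extra cut-off against later PRRT. The last scheduled sample is at 24 h, follow-up ends with the 48 h call, and protocol section 6 does not permit PRRT until at least 7 days after the infusion. A third laboratory window is not needed.

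**Conclusion.** The conflict stands in the current text, and the size is minor. Applied as written, the cut excludes valid 24 h samples from the worst-grade tables, the shift tables and the single-parameter liver counts. It also contradicts the period that SAP 2.1.1 sets for safety summaries.

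This conclusion rests on a literal, elapsed-time reading and on SAP 2.7.3 overriding 2.1.1. If either fails, no compliant 24 h sample is lost. It would be wrong to infer from the 2-of-4-hours figure that half the patients drop out of the tables.

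All laboratory values are listed, with a separate listing of grade 3 or 4 values, and clinically relevant changes are recorded as adverse events. The 2–12 h electrolyte and blood gas samples are untouched. The primary potassium analysis is specified separately in SAP 2.5 and does not depend on this sentence.

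**What to change.** Replace the cut-off sentence in SAP 2.7.3 with two sentences to this effect:

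*Laboratory summaries by time point include samples up to and including the nominal 24 h time point, slotted as in Section 2.1.1; this covers 24 h samples drawn more than 24 hours after infusion start. The worst-value, shift and liver tables use every post-baseline value in the on-treatment period defined in Section 2.1.1.*

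The first sentence removes the clash with the ±2 h window. The second removes the clash with the 30-day period and settles that repeat samples after the 24 h visit count. The cost is one SAP sentence replaced by two, before database lock, with no new data and no protocol amendment. If the nominal visit was always meant, the first sentence changes no output.
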